# Appendix 2: Study Flowchart

Assessment	Screening	Exon 19 deletion or exon 21 substitution L858R in the TK domain of EGFR gene	Treatment Period		Final Visit / Withdrawal from Treatment	Safety Follow-up Visit k	Off-study Visit
	Days		Visit # (Day 1 of every 8 th week throughout treatment period)		End of Study Treatment	End of study ( 28 days after last study drug administration)	Survival follow-up every 6 th months h
	-21 to -1		Visit 1 (Baseline)	Visit – every 8 th week, until PD, death, unacceptable toxicity or patient’s decision			
Visit Window	≤ 21 days		0	+/- 5 days	+/- 5 days	+/- 5 days	+/- 15 days
Informed consent	X						
EGFR Testing	X						
Medical history	X						
Pregnancy test a	X		X		X		
Physical examination b	X		X	X	X	X	
ECOG PS	X		X	X	X	X	
ECG c	X		To be repeated as clinically indicated				
Demographics	X						
Haematology	X		X	X	X	X	
Biochemistry	X		X	X	X	X	
Coagulation	X j						
Concomitant medications	X		X	X	X	X	
Tumour assessment d			X	X	X		
Adverse events e	X		X	X	X	X	X
Subsequent therapy for NSCLC f						X	X
Drug dispensing and accountability g			X	X	X i		

Notes: First dose of study drug to be taken as soon as positive EGFR mutations test result has been received and appropriate drug has been provided.

a Urine or blood.

b Including an ophthalmologic examination if clinically indicated.

c At baseline and as clinically indicated throughout the study.

d Tumour assessment consists at minimum of a CT scan of chest and upper abdomen (for imaging of liver and adrenal glands). Patients known to have bone metastasis or displaying clinical or laboratory signs (e.g. serum alkaline phosphatase (ALP) > 1.5 ULN) of bone metastasis should have an isotope bone scan at baseline. Brain CT scan or MRI is not mandatory but should be done if there is a clinical suspicion of cerebral metastasis. Post-baseline assessments are to be performed within +/- 5 days for the 8 weekly assessments. If there is

suspicion of disease progression based on clinical or laboratory findings, a tumour assessment should be performed as soon as possible, before the next scheduled evaluation.

e Graded according to NCI CTC-AE version 4.0. During screening period only SAEs caused by a protocol-mandated intervention will be collected (e.g., SAEs related to invasive procedures such as biopsies, medication washout, or no treatment run-in). During the study, and until Safety Follow-up visit all SAEs and AEs of special interest will be collected and reported. After Safety Follow up visit all SAEs and AEs of special interest related with the study drug, will be collected and reported.

f Subsequent therapy for all patients.

g For details on drug dispensing and accountability see Section 6. of the Protocol.

h or as appropriate.

i Drug returning and final accountability.

j To be obtained in the 7 days before study treatment initiation for the patients taking anti-coagulants.

k To be performed 28 days after the last study drug administration.

## Appendix 3: Derived Variables

The following variables will be derived:

### Screening visit

**Age:** The difference between the screening visit date and the patient's birth date, in whole years.

**Duration of disease:** The difference between the screening visit date and the date of NSCLC diagnosis, in whole years.

**Smoking duration (in years):** For ex-smokers is the difference between the start and stop year (in years) of smoking and for smokers is the difference between the start year and the screening visit year.

**Stage TNM:** a categorical variable will be obtained. The following criteria will be considered:

Occult Carcinoma – TX, N0, M0;

Stage 0 – Tis N0 M0;

Stage IA – T1a N0 M0;

Stage IB – T1b N0 M0;

Stage IIA – T2b N0 M0 or T1a N1 M0 or T1b N1M0 or T2a N1 M0;

Stage IIB – T2b N1 M0 or T3 N0 M0;

Stage IIIA – T1a N2 M0 or T1b N2 M0 or T2a N2 M0 or T2b N2 M0 or T3 N1 M0 or T3 N2 M0 or T4 N0 M0 or T4 N1 M0;

Stage IIIB – T1a N3 M0 or T1b N3 M0 or T2a N3 M0 or T2b N3 M0 or T3 N3 M0 or T4 N2 M0 or T4 N3 M0;

Stage IV – Any T, any N and M1a or Any T, any N and M1b.

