antagonist such as ranitidine should be considered and used in a staggered manner. Erlotinib must be taken at least 2 hours before or 10 hours after the H₂-receptor antagonist dosing. International Normalized Ratio (INR) elevations and bleeding events, including gastrointestinal bleeding, have been reported in clinical studies, some associated with concomitant warfarin administration. Coumarins (SintromTM; VarfarinTM) use is an exclusion criterion. If the patient requires anti-coagulation therapy, then the use of low molecular weight heparin instead of coumarins is recommended where clinically possible. In a phase Ib study, there were no significant effects of gemcitabine on the pharmacokinetics of erlotinib nor were there significant effects of erlotinib on the pharmacokinetics of gemcitabine (Core data sheet, 2009).

The following potent CYP3A4 inhibitors may *increase* erlotinib toxicity:

Systemic antifungals (e.g. ketoconazole, itraconazole, miconazole).

Erythromycin, clarithromycin, troleandomycin.

Selective serotonin reuptake inhibitors (e.g. nefazodone).

The following medications could decrease plasma levels of erlotinib and hence decrease efficacy, but they probably do not represent a safety concern:

- Antiepileptics (e.g. carbamazepine, phenobarbital, phenytoin).
- Rifampin, rifabutin.
- Troglitazone.
- Barbiturates.
- Glucocorticoids.
- Saint John's wort.

21. Appendix 4: 7th Edition AJCC Cancer Staging Manual - Part IV

Lung

(Carcinoid tumors are included. Sarcomas and other rare tumors are not included.)

At-A-Glance

SUMMARY OF CHANGES

- This staging system is now recommended for the classification of both non-small cell and small cell lung carcinomas and for carcinoid tumors of the lung
- The T classifications have been redefined:
 - T1 has been subclassified into T1a (≤ 2 cm in size) and T1b (>2 –3 cm in size)
 - T2 has been subclassified into T2a (>3 –5 cm in size) and T2b (>5 –7 cm in size)
 - T2 (>7 cm in size) has been reclassified as T3
 - Multiple tumor nodules in the same lobe have been reclassified from T4 to T3
 - Multiple tumor nodules in the same lung but a different lobe have been reclassified from M1 to T4
- No changes have been made to the N classification. However, a new international lymph node map defining the anatomical boundaries for lymph node stations has been developed
- The M classifications have been redefined:
 - M1 has been subdivided into M1a and M1b

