Table 25.2 shows a comparison of the 6th edition and 7th edition TNM for lung cancer to assure clarity for the user. The final 7th edition TNM is described in the “Definitions of TNM” section that follows.

PROGNOSTIC FEATURES

The IASLC lung cancer database, although retrospective, provides the largest published analyses of prognostic factors in both NSCLC and SCLC. Potentially useful prognostic variables for lung cancer survival that were considered included: TNM

[figure not shown]

FIGURE 25.5. Survival in all SCLC by TNM stage (according to “best” stage based on a combination of clinical and pathologic staging in the IASLC lung database).

“Used with the permission of the American Joint Committee on Cancer (AJCC), Chicago, Illinois. The original source for this material is the AJCC Cancer Staging Manual, Seventh Edition (2010) published by Springer Science and Business Media LLC, www.springer.com.”

TABLE 25.2. Stage grouping comparisons: 6th edition vs. 7th edition descriptors, T and M categories, and stage groupings

Sixth edition T/M descriptor	7th edition T/M	N0	N1	N2	N3
T1 (≤2 cm)	T1a	IA	IIA	IIIA	IIIB
T1 (>2–3 cm)	T1b	IA	IIA	IIIA	IIIB
T2 (≤5 cm)	T2a	IB	IIA	IIIA	IIIB
T2 (>5–7 cm)	T2b	IIA	IIB	IIIA	IIIB
T2 (>7 cm)	T3	IIB	IIIA	IIIA	IIIB
T3 invasion	T3	IIB	IIIA	IIIA	IIIB
T4 (same lobe nodules)	T3	IIB	IIIA	IIIA	IIIB
T4 (extension)	T4	IIIA	IIIA	IIIB	IIIB
M1 (ipsilateral lung)	T4	IIIA	IIIA	IIIB	IIIB
T4 (pleural effusion)	M1a	IV	IV	IV	IV
M1 (contralateral lung)	M1a	IV	IV	IV	IV
M1 (distant)	M1b	IV	IV	IV	IV

Cells in bold indicate a change from the 6th edition for a particular TNM category.

stage, tumor histology, patient age, sex, and performance status, various laboratory values and molecular markers.

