**Table 4 – Medical history: NSCLC Diagnosis – ITT population**

	Total (n=xx)
Duration of disease (years)	
N	
Mean	
Median	
Standard Deviation	
Minimum	
Maximum	
Diagnosis technique, n (%)	
Histology - Bronchoscopy	
Histology - Other	
Cytology - Sample FNA (Fine Needle Aspirate)	
Cytology - Sputum	
Cytology - Pleural effusion	
Cytology - Other	
Total	
Patology results, n (%)	
Adenocarcinoma	
Bronchoalveolar carcinoma	
Large cell carcinoma	
Squamous cells carcinoma	
Mixed cell type	
Other	
TNM classification: T, n (%)	
X	
0	
is	
1a	
1b	
2	
3	
4	
Total	
TNM classification:N, n (%)	
X	
0	
1	
2a	
2b	
3	
Total	
TNM classification:M, n (%)	
X	
0	
1a	
1b	
Total	

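### The SAP's stage I rules contradict the protocol's AJCC 7 appendix, and the T and N rows of Table 4 match neither; the effect is confined to M0 patients in a descriptive table

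*SAP*

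**What the plan says.** SAP Appendix 3 (Derived Variables, Screening visit) defines a categorical stage variable. Its stage I and IIA rules are:

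- for the lowest group, with a single combination listed: "Stage IA – T1a N0 M0"
- for the next group, again with a single combination listed: "Stage IB – T1b N0 M0"
- for the group after that, where T2a first appears: "Stage IIA – T2b N0 M0 or T1a N1 M0 or T1b N1M0 or T2a N1 M0"

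Stage IV is "Stage IV – Any T, any N and M1a or Any T, any N and M1b". T2a occurs in the rules with N1, N2 and N3, never with N0.

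Protocol Appendix 4 reproduces the AJCC 7th edition lung chapter. Its summary of changes says that "T2 has been subclassified into T2a" and T2b, and its N definitions contain one N2 category. Table 25.2 there gives the stage for each T category, with columns N0, N1, N2 and N3. The row for T1b reads "T1 (>2–3 cm) T1b IA IIA IIIA IIIB"; the row for T2a reads "T2 (≤5 cm) T2a IB IIA IIIA IIIB".

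The SAP Table 4 shell lists T as X, 0, is, 1a, 1b, 2, 3, 4. Under "TNM classification:N, n" it lists X, 0, 1, 2a, 2b, 3. Its continuation prints a row for each derived stage, including IA and IB.

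**The concern.** Two rules of a stated derivation disagree with the staging system that the protocol itself supplies. If programmed as written, a T1b N0 M0 patient is reported one stage too high and a T2a N0 M0 patient has no stage. The Table 4 rows add a second inconsistency: the a/b split appears to have been placed on N instead of T, so the shell agrees neither with the SAP's rules nor with AJCC 7.

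What is at stake is the description of the patients to whom a single-arm response rate applies. With about 30 patients, each one misfiled or unstaged is 1/30 = 3.3% of the table. The same table is part of the interim characterisation, because SAP sections 5.5 and 6.12 include medical history.

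**Working it through.** No sample size, power or error rate is involved. The check is a comparison of two sets of rules, followed by a test of whether the Table 4 categories fit the SAP rules.

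**Step 1: SAP rules against the protocol grouping, M0 only.** Table 25.2 covers six T categories (T1a, T1b, T2a, T2b, T3, T4) by four N categories: 6 × 4 = 24 combinations. Adding TX N0 (occult) and Tis N0 (stage 0) gives 26. The SAP has rules for 25 of them.

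| Combination | Protocol Appendix 4 | SAP Appendix 3 |
|---|---|---|
| T1b N0 M0 | IA | IB |
| T2a N0 M0 | IB | no rule |
| other 24 | – | same as protocol |

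So 24 of 26 agree. All 15 stage III rules (8 IIIA, 7 IIIB) are among those that agree.

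**Step 2: Table 4 categories read literally against the SAP rules.** Taking T1a, T1b, T2, T3, T4 by N0, N1, N2a, N2b, N3 at M0 gives 5 × 5 = 25 cells.

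- The whole T2 row fails, because the rules name only T2a and T2b: 5 cells.
- N2a and N2b fail for the other four T rows, because the rules name only N2: 4 × 2 = 8 cells.
- Total with no matching rule: 5 + 8 = 13. The other 12 match a rule.

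Counted by rule instead, 8 of the 15 stage III rules name N2, T2a or T2b: T1a N2, T1b N2, T2a N2, T2b N2 and T3 N2 in IIIA; T2a N3, T2b N3 and T4 N2 in IIIB.

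**Step 3: N2a and N2b read as N2.** This leaves 5 × 4 = 20 cells. The unsplit T2 row becomes:

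| Cell (M0) | Protocol grouping | SAP rules as written |
|---|---|---|
| T2 N0 | IB or IIA | none or IIA |
| T2 N1 | IIA or IIB | IIA or IIB |
| T2 N2 | IIIA | IIIA |
| T2 N3 | IIIB | IIIB |

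Every stage III cell now has one stage. Only T2 N0 and T2 N1 remain undetermined, so 18 of 20 cells resolve.

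**Step 4: M1.** Any M1a or M1b patient is stage IV whatever the T and N codes, so neither discrepancy reaches metastatic patients.

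**Step 5: after correction.** With IA = T1a or T1b N0 M0 and IB = T2a N0 M0, all 26 combinations agree. With T2a, T2b and a single N2 as categories, all 24 combinations of T1a–T4 by N0–N3 at M0 receive exactly one stage.

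**The case against.** The best reply is that the errors lie where this trial has few patients. Eligibility requires inoperable, locally advanced or metastatic disease, and the sample-size section counts stage IIIB and IV cases. Both wrong rules are stage I cells. Stage is a frequency in a baseline table: ORR, PFS, OS and response duration do not use it, and the only efficacy subgroup is exon 19 versus 21. All of this stands, and it caps the importance of the point.

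It does not show that the stage I cells are empty. Protocol section 1.3 includes recurrent disease among the patients to be tested, and exclusion criterion 1 allows adjuvant or neo-adjuvant therapy that ended at least six months before entry. TNM is reported under the NSCLC diagnosis heading in SAP section 5.3.4.1. Against that, Appendix 3 lists the stage variable under the screening visit, and the documents do not say when TNM is taken. That early-stage cells are reached through TNM recorded at an earlier diagnosis is therefore an assumption.

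A reader might also infer from Step 2 that Table 4 cannot feed the derivation and that more than half of the stage III rules fail. The documents do not support this. Table 4 is an empty output shell; stage is derived from patient data, and the CRF coding is not shown. The 8-of-15 count is a mismatch of labels that reading N2a and N2b as N2 removes completely.

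**Conclusion.** The point holds as a transcription error in a derivation. SAP Appendix 3 gives T1b N0 M0 the wrong stage and T2a N0 M0 none, and the T and N rows in Table 4 are inconsistent with both the derivation and AJCC 7. It is worth correcting, but it is minor.

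The size is two of 26 M0 combinations. If the CRF also recorded T2 without the split, T2 N0 M0 and T2 N1 M0 could not be staged either. The number of patients involved cannot be computed, because neither the TNM time point nor the CRF coding is given. The tempting broader conclusion, that baseline stage as a whole will be wrong or missing, does not follow: stage IV is unaffected, the stage III rules are correct, and only M0 patients in a descriptive table can be touched.

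**What to change.** 1. In SAP Appendix 3, set IA = T1a N0 M0 or T1b N0 M0, and IB = T2a N0 M0.
2. Before programming, check how the CRF codes T and N. This decides whether Table 4 is only a misprint or reflects what was collected.
3. In Table 4, show T2a and T2b and a single N2. If N2a and N2b were recorded, collapse them to N2. If T2 was recorded unsplit, relabelling cannot recover the split: report T2 N0 M0 and T2 N1 M0 as not stageable.
4. State in SAP section 5.3.4.1 whether TNM refers to original diagnosis or to study entry.

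The cost is two derivation lines, one table shell, one sentence and a look at the CRF. The correct grouping is already in Protocol Appendix 4, and no efficacy analysis changes.

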### Treatment period

**Response duration:** It will be measured from the time of initial response (CR/PR whichever is first recorded) until documented tumor progression (in weeks).

**Best overall response:** a categorical variable will be obtained, defined as the best response across all time points, according to RECIST 1.1, until end of study treatment. The following criteria will be considered:

Complete response – Patients who presented at least one complete response;

Partial response – Patients who not presented a complete response and presented at least one partial response;

Stable disease – Patients who not presented response (complete or partial) and presented at least one stable disease;

Progression disease – Patients who not presented response or stable disease and presented progression disease;

Inevaluable – All assessments are inevaluable.

**Objective response:** A dichotomous variable (yes/no) will be calculated. Patients who presented complete response or partial response as the best overall response will be classified in “yes”. Otherwise patients will be classified in “no”.

**Event PFS:** A dichotomous variable (yes/no) will be calculated. Patients who presented progression disease or death for any cause will be classified in “yes”. Otherwise patients will be classified in “no”.

**Time PFS:** Time between baseline visit and date of first occurrence of disease progression or death for any cause (in weeks) while the patient was under study or during the prolonged follow-up period. In patients where disease progression or death from any cause was not observed, the time will be censored at the date of last visit or last contact with the patient.

**Time overall survival:** The time from the first dose of erlotinib (assumed to be baseline visit) to the date of death due to any cause (in weeks). For patients alive at the end of the follow-up period, the time was censored at the date of last visit or last contact with the patient.

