4.3. Best overall response: all time points

The best overall response is determined once all the data for the patient is known.

Best response determination in trials where confirmation of complete or partial response IS NOT required: Best response in these trials is defined as the best response across all time points (for example, a patient who has SD at first assessment, PR at second assessment, and PD on last assessment has a best overall response of PR). When SD is believed to be best response, it must also meet the protocol specified minimum time from baseline. If the minimum time is not met when SD is otherwise the best time point response, the patient's best response depends on the subsequent assessments. For example, a patient who has SD at first assessment, PD at second and does not meet minimum duration for SD, will have a best response of PD. The same patient lost to follow-up after the first SD assessment would be considered invaluable.

Best response determination in trials where confirmation of complete or partial response IS required: Complete or partial responses may be claimed only if the criteria for each are met at a subsequent time point as specified in the protocol (generally 4 weeks later). In this circumstance, the best overall response can be interpreted as in Table 3.

Table 3 – Best overall response when confirmation of CR and PR required.

Overall response First time point	Overall response Subsequent time point	BEST overall response
CR	CR	CR
CR	PR	SD, PD or PR ^a
CR	SD	SD provided minimum criteria for SD duration met, otherwise, PD
CR	PD	SD provided minimum criteria for SD duration met, otherwise, PD
CR	NE	SD provided minimum criteria for SD duration met, otherwise NE
PR	CR	PR
PR	PR	PR
PR	SD	SD
PR	PD	SD provided minimum criteria for SD duration met, otherwise, PD
PR	NE	SD provided minimum criteria for SD duration met, otherwise NE
NE	NE	NE

CR = complete response, PR = partial response, SD = stable disease, PD = progressive disease, and NE = invaluable.

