4.6.1. Confirmation

In non-randomized trials where response is the primary endpoint, confirmation of PR and CR is required to ensure responses identified are not the result of measurement error. This will also permit appropriate interpretation of results in the context of historical data where response has traditionally required confirmation in such trials. However, in all other circumstances, i.e. in randomized trials (phase II or III) or studies where stable disease or progression are the primary endpoints, confirmation of response is not required since it will not add value to the interpretation of trial results. However, elimination of the requirement for response confirmation may increase the importance of central review to protect against bias, in particular in studies which are not blinded.

In the case of SD, measurements must have met the SD criteria at least once after study entry at a minimum interval (in general not less than 6–8 weeks) that is defined in the study protocol.

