## **5.3 ANALYSIS OF STUDY CONDUCT**

A descriptive analysis of all study variables will be done. For continuous variables, the mean, standard deviation (SD), median, maximum and minimum will be computed whereas for categorical variables the absolute (n) and relative frequencies (%) will be described.

All analyses will be performed using SAS version 9.4 (SAS Institute Inc, Cary, USA).

All derived variables to be used in the analysis are described in Appendix 3.

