#### 5.3.9.1 Primary Efficacy Endpoint

The primary efficacy endpoint is the objective response rate (ORR) defined by the number of patients with complete response (CR) or partial response (PR) as the best overall response during the treatment period divided by the total number of patients based on diagnostic imaging according to RECIST 1.1 (see Appendix 5). The ninety five percent (95%) confidence interval will be estimated for the ORR.

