### **4. Evaluation of best overall response**

The best overall response is the best response recorded from the start of the study treatment until the end of treatment taking into account any requirement for confirmation. On occasion a response may not be documented until after the end of therapy so protocols should be clear if post-treatment

assessments are to be considered in determination of best overall response. Protocols must specify how any new therapy introduced before progression will affect best response designation. The patient's best overall response assignment will depend on the findings of both target and non-target disease and will also take into consideration the appearance of new lesions. Furthermore, depending on the nature of the study and the protocol requirements, it may also require confirmatory measurement. Specifically, in non-randomized trials where response is the primary endpoint, confirmation of PR or CR is needed to deem either one the 'best overall response'. This is described further below.

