#### **4.6. Confirmatory measurement/duration of response**

##### **4.6.1. Confirmation**

In non-randomized trials where response is the primary endpoint, confirmation of PR and CR is required to ensure responses identified are not the result of measurement error. This will also permit appropriate interpretation of results in the context of historical data where response has traditionally required confirmation in such trials. However, in all other circumstances, i.e. in randomized trials (phase II or III) or studies where stable disease or progression are the primary endpoints, confirmation of response is not required since it will not add value to the interpretation of trial results. However, elimination of the requirement for response confirmation may increase the importance of central review to protect against bias, in particular in studies which are not blinded.

In the case of SD, measurements must have met the SD criteria at least once after study entry at a minimum interval (in general not less than 6–8 weeks) that is defined in the study protocol.

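### SAP Appendix 3 counts any single CR or PR as response and labels this RECIST 1.1, but the RECIST text appended to both documents requires confirmation in this design, so the primary ORR can only equal or exceed the confirmed ORR

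*SAP*

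**What the plan says.** SAP 5.3.9.1 defines the primary ORR as the number of patients with CR or PR as best overall response, "divided by the total number of patients based on diagnostic imaging according to RECIST 1.1 (see Appendix 5"). SAP 5.3 makes Appendix 3 the operative rule: "All derived variables to be used in the analysis are described in Appendix 3". Under Treatment period, Appendix 3 assigns CR to a patient with one CR at any time point and PR to "Patients who not presented a complete response and presented at least one partial response". It states that this follows RECIST 1.1.

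The RECIST 1.1 text in SAP Appendix 5 says, in section 4, that "in non-randomized trials where response is the primary endpoint, confirmation of PR or CR is needed to deem either one" the best overall response. Its section 4.6.1 begins "In non-randomized trials where response is the primary endpoint, confirmation of PR and CR is" and continues that this is required. Protocol Appendix 1, section 4.6.1, has the same rule and gives measurement error as the reason: "In non-randomized trials where response is the primary endpoint, confirmation of PR and CR is required to ensure responses identified are not the result".

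Section 4.3 of the same text separates two kinds of trial. Where confirmation is not required, "Best response in these trials is defined as the best response across all time points". Where it is required, the response criteria must be met a second time, generally 4 weeks later, and the interval is left to the protocol.

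Protocol 8.1.1 defines ORR as CR or PR observed per RECIST 1.1. It neither mentions nor waives confirmation. Neither document sets a confirmation interval or plans a confirmed analysis.

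**The concern.** The trial is single-arm and its primary endpoint is response, so the appended text puts it in the group that needs confirmation. Appendix 3 applies the rule for the other group under the same RECIST 1.1 label. A programmer who follows Appendix 3 exactly will produce a primary estimate that is not the RECIST 1.1 response rate for this design.

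At stake are the primary estimate and its 95% CI, the comparison with published data planned in Protocol 3.3, and the set of patients entering the response-duration analysis. The appended text also notes that dropping confirmation can make central review more important, particularly without blinding. This trial is open-label, and Protocol 8.1.3 gives an independent review committee as not applicable.

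**Working it through.** **Does the confirmation condition apply?** Protocol 3.1 calls the trial non-randomized, Protocol 6.4 calls it open-label and single-arm, and Protocol 8.1.1 makes ORR primary. Both conditions in section 4.6.1 of the RECIST text are met.

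**Side by side.**
- RECIST text for this design: CR or PR counts only if seen again at a later time point (section 4.3 and its Table 3).
- SAP Appendix 3: one CR or PR is enough, with no later scan needed.

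**The plan's own figure.** SAP 5.1 gives n = 30 and a margin of about ±17.5 points. The Wald half-width is 1.96 × √(p(1 − p)/30). At p = 0.6 or 0.4 it is 17.5 points; at p = 0.5 it is 17.9. The stated margin is reproduced, although the SAP gives no p. It describes sampling error only and says nothing about the gap between the two response rules.

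**Direction.** Let A be the number of patients with at least one CR or PR, C the number with a confirmed CR or PR, and N the common denominator. A confirmed response contains at least one CR or PR, so every patient in C is in A, and C/N ≤ A/N. As a check, every sequence of CR, PR, SD, PD and NE of length 1 to 6 was classified by both rules. Confirmation there meant CR or PR again at the next evaluable time point before PD, with NE skipped. Of 5 + 25 + 125 + 625 + 3,125 + 15,625 = 19,530 sequences, none was confirmed but missed by Appendix 3, and 11,354 were counted by Appendix 3 but not confirmed. These counts show direction only, because the sequences are not equally likely in patients.

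**Size.** Each unconfirmed responder adds 100/30 = 3.3 points. The documents give no share of unconfirmed responses, so the following range is an assumption. It starts from 21/30, close to the 70.6% quoted in Protocol 1.3. Intervals are Clopper-Pearson, one reading of the binomial interval in Protocol 8.2.1.1.

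| Assumed unconfirmed, of 21 | Confirmed ORR | 95% CI |
|---|---|---|
| 0 | 21/30 = 70.0% | 50.6 to 85.3 |
| 1 | 20/30 = 66.7% | 47.2 to 82.7 |
| 2 | 19/30 = 63.3% | 43.9 to 80.1 |
| 4 | 17/30 = 56.7% | 37.4 to 74.5 |

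**Feasibility.** Scans are 8-weekly within ±5 days (Protocol 5.3), so consecutive on-schedule scans are at least 56 − 5 − 5 = 46 days apart, which exceeds 28. Unscheduled and end-of-treatment scans can fall closer.

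**The case against.** The rule is not hidden. Appendix 3 states it openly in advance, and a programmer can apply it without guessing. Protocol 8.1.1 speaks of response being observed, and no confirmation interval is set although the RECIST text leaves that to the protocol. An unconfirmed endpoint may be what the sponsor intended. That much stands: a reader might infer concealment or an unworkable definition, and the documents support neither. What is missing is a sentence reconciling the rule with the text it cites.

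Nor can the appendix be set aside as generic reference material. Protocol 5.3 has response evaluated by RECIST as given in its Appendix 1, and SAP 5.3.9.1 ties the primary endpoint to Appendix 5. The sentence in Protocol 8.1.1 that speaks of observed response also invokes RECIST 1.1.

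Other tempting readings go too far:
- **A large excess, or one due only to measurement error.** No number of unconfirmed responders can be derived. Genuine responses followed by progression, death, treatment stop or data cut-off before a second scan are also unconfirmed.
- **A compromised test.** Protocol 8.2.2 has no hypothesis test, so no error rate changes.
- **A demonstrably unfair comparison with published rates.** The documents quote 70.6% and 82.9% without saying whether either was confirmed. The 82.9% comes from an Asian population, whereas Protocol 3.3 names a Caucasian comparator.

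**Conclusion.** The point holds as an internal contradiction in the primary endpoint and should be fixed. The Appendix 3 ORR equals or exceeds the confirmed ORR for any data, provided both use the same denominator, as they would within ITT and within PP. The gap is 3.3 points per unconfirmed responder if 30 patients are analysed; the total is unknown and may be zero. The consequence is confined to estimation: the primary ORR and its CI, the comparison with published data, and the population for response duration.

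**What to change.** The following needs SAP text, tables and programming only.

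1. State in SAP 5.3.9.1 and Appendix 3 that the any-single-response rule departs from the confirmation requirement in Appendix 5, and why. Label that ORR unconfirmed in Tables 10 and 11.
2. Report confirmed ORR with its 95% CI beside it in both tables, on the same denominator. Patients without confirmation stay in as non-responders; the omission rule in SAP 5.4 must not remove them. Define confirmed as follows:
   - CR or PR at one assessment and again at a later one at least 4 weeks after it. Four weeks is the interval the RECIST text calls general, and the SAP should flag it as a choice.
   - Use actual scan dates, because SAP 5.3.7 assigns off-schedule scans to the nearest visit.
   - No SD or PD at any scan in between, scheduled or not. NE in between is allowed, as section 4.4 of the RECIST text suggests.
   - PR then CR counts as PR, as in Table 3 of Protocol Appendix 1.
   - CR then PR follows Table 3 and its footnote: PR only if the original CR is reclassified as PR, otherwise not a response.
   - Show unconfirmed CR/PR as its own line in Tables 10 and 11. Table 3 would otherwise need a minimum SD duration, which neither document defines.
3. Report response duration (Tables 18 and 19) for confirmed responders as well, measured from the date the criteria were first met (section 4.6.2 of the RECIST text).

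Making confirmed ORR the primary result is the reading that matches Appendix 5. It needs an amendment to Protocol 8.1.1, approved under Protocol section 12 before it is implemented.

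No extra scans are needed. The costs are that the confirmed ORR may be lower and that late responses may stay unconfirmed. If the primary definition is changed after responses are known in this open-label trial, the change must be dated and both versions reported.
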